Title page

Protocol Title: Pseudoephedrine Prophylaxis for Prevention of Middle Ear Barotrauma in Hyperbaric Oxygen Therapy NCT Study No.: NCT04332211

Principal Investigator: [name] Revised Sudafed Study Protocol Date: 1/17/22

Protocol

The initial study design employed a 1:1 pseudoephedrine to placebo ratio. At exactly half enrollment (42 out of 84) the research team recognized that the capsule prepared requires 15 minutes to be dissolved, in addition to the 20-30 minutes it takes for the pseudoephedrine tablet to be absorbed and take effect. Therefore, the following two changes have been applied to the protocol: 1. The study capsule will be administered 45 minutes prior to initiation of hyperbaric oxygen therapy; 2. The ratio of pseudoephedrine to placebo will be changed to 2:1 starting with enrollment #43; The total number of enrollments will be increased from 84 to 105. (Because the participants who received the Sudafed tablet did not have enough time for the study capsule and tablet to be digested and take effect we can not use their data for a reliable comparison of Sudafed to placebo. To reiterate, we have enrolled 21 with placebo, and 21 with badly-timed Sudafed. Overall, we need 42 with placebo and 42 with well-timed Sudafed based on our power calculation. Thus, we need another 21 (placebo) and 42 (well-timed Sudafed). This will require us to enroll another 63 patients with a 2:1 ratio. Thus we will need to increase the total number of participants we enroll for the protocol because the initial 21 with badly-timed Sudafed can not be used in the direct comparison calculations. In summary, in order to increase the number of Sudafed enrolled patients, we plan to change the enrollment ratio starting with #43 to 2 (Sudafed) to 1 (placebo). To reach statistical significance, based on our power calculation, we will need to increase our enrollment to a total of 105 (from initial 84) with the next 63 capsules packaged in the 2 Sudafed to 1 placebo ratio.)

Additionally, given the December 2021 RNI IRB recommendations, [name] (PI) will be the only study member who reviews and sings the eligibility criteria checklist for each enrolled participant (this was the case previously, but now is officially in the protocol)

Research Design and Methods

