Trained research assistants will approach patients scheduled for their initial HBOT. If the patient is interested in participation, informed consent will be obtained. A copy of the informed consent will be given to the patient, and the signature page will be collected and kept in a secure location. Enrolled patients will be de-identified and assigned a consecutive study number starting with the number one. A record on the total number of potential eligible participants approached will also be kept. In order to confirm decision making capacity, the patient will be asked the following three questions prior to signing the consent form: 1. Why are we doing this study?; 2. What medication are we testing in this study?; 3. Who can you contact if you have further questions about the study? If the patients are able to answer these questions and the attending hyperbaric physician has them sign an informed consent form for the scheduled hyperbaric therapy, then they are deemed competent to be enrolled in the study. In order to prevent enrolling pregnant patients, the attending hyperbaric physician will be asked to check the result of the pregnancy test. If positive, or not available in a female patient of child bearing age, the patient will be excluded from the study. The PI will be the only study member who will review and sign the eligibility criteria for each enrolled participant.

Protocol:

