The sample size of 42 was calculated for enrollment into each group (use of pseudoephedrine, no use of rescue pseudoephedrine) to detect a significant difference in pain score between the treated and untreated groups. We use the standard Alpha=0.05, and power of 80%. This calculation was based on the incidence of barotrauma in placebo groups based on prior publications in scuba divers (32%). The incidence in pseudoephedrine treated group was 8%.

Sample Size	
Group 1	42
Group 2	42
Total	84
Study Parameters	
Incidence, group 1	32%

Incidence, group 2	8%
Alpha	0.05
Beta	0.2
Power	0.8

We will screen 90 patients (5% oversample) to obtain the required subjects in each group.

The primary outcome variable will be the frequency of severe pain and need for oxymetazoline rescue therapy, between the two groups. These frequencies will be compared using chi-square or Fisher's exact test, as appropriate. We will calculate 95% confidence intervals for the difference in frequencies between groups using normal binomial approximation.

Model building will be based on the results of the univariate analysis of independent and outcome variables. During model building, we will also test variables in a stepwise fashion into the model to identify confounders and effect modifiers. We will then use logistic regression analysis to build the final model between our independent variables to our dependent or outcomes variable.

Timeline:

IRB application will be completed by mid-April 2020.

Medical student and RN research assistant will complete CITI training and be added to the IRB protocol by May 2020

UMMC Investigational drug pharmacy will be notified about the need for manufacturing and deidentification of placebo and pseudoephedrine by mid-April 2020.

Study will be registered with ClinicalTrials.gov by May 2020.

Patient enrollment will begin by mid May 2020 (end of first year of medical school)

We anticipate reaching goal of 84 enrolled patients prior to November 2020.

Data analysis and abstract will be complete by February 2021.

Manuscript will be submitted to Undersea and Hyperbaric Medicine Journal by March 2021.

Limitations:

Given the small sample size, it is possible that some factors, measured or unmeasured, that may affect ear pain or request for rescue therapy will randomly differ between pseudoephedrine and placebo groups. Such factors may bias the study.

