Our comparisons were based on our primary outcome measures (pain ratings, Teed scores, and oxymetazoline rescue therapy) between placebo and pseudoephedrine. Our sample size, based on power 0.8, significance 0.05, and effect size 8% versus 32%, was 42 patients in each group. The effect size was based on barotrauma measured in SCUBA divers [10]. Initial allocation was 1:1, but by the 42nd enrollment, we learned that the capsules prepared by the investigational drug pharmacy required additional dissolution time, necessitating a 45-minute wait rather than the original 30-minute protocol. Because of inadequate time for drug effect, patients assigned pseudoephedrine up to that point were not considered for the primary outcome comparison. Thus, we subsequently changed our allocation to 2:1 to increase the number receiving pseudoephedrine, starting with subject #43. This increased our total enrollment from 84 to 105.

For comparisons of placebo versus pseudoephedrine, we used only subjects with pseudoephedrine ingested at least 45 minutes before HBO2 treatment. We used data from subjects provided pseudoephedrine less than 45 minutes before treatment only for estimates of the incidence of complications of HBO2 treatment.

We compared frequencies of primary outcome measures using chi-square or Fisher's exact test, as appropriate. We calculated 95% confidence intervals for the difference in frequencies between categories using normal binomial approximation. We compared ordinal variables using the Wilcoxon rank sum test.

We used logistic regression to adjust for potential confounding by baseline variables (age, sex, HBO2 pressure, history of obstruction, sinus disease, smoking, and inpatient status). We used backward selection, aiming for a precise and unbiased estimate of the pseudoephedrine effect. We removed only variables whose removal would not change this estimate by >10% or increase the standard error by >20%.

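### Half the planned placebo group was enrolled before any analysed pseudoephedrine patient, and neither the primary test nor the sparse, data-selected logistic model allows for it

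*Combined protocol and SAP*

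**What the plan says.** The opening Protocol section (revision dated 17 January 2022) states "we have enrolled 21 with placebo, and 21 with badly-timed Sudafed". It counts those 21 placebo patients towards a target of 42 per group, and plans a further 21 placebo and 42 pseudoephedrine patients at 2:1 from #43. The Statistical analysis section of the manuscript methods confirms that "patients assigned pseudoephedrine up to that point were not considered for the primary outcome comparison".

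The primary comparison is chi-square or Fisher's exact test, with a normal-approximation interval for the risk difference. The manuscript methods then adjust by logistic regression for "baseline variables (age, sex, HBO2 pressure, history of obstruction, sinus disease, smoking, and inpatient status", using backward selection and "aiming for a precise and unbiased estimate of the pseudoephedrine effect". The removal rule is: "We removed only variables whose removal would not change this estimate by >10% or increase the standard error by >20" per cent. The protocol's own Statistical analysis section describes another route, in which "we will also test variables in a stepwise fashion into the model to identify confounders and effect modifiers", followed by logistic regression "to build the final model between our independent variables to our dependent or outcomes variable".

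No section contains a period term, a stratified test or an analysis restricted to concurrent patients. Under Limitations, the protocol considers only chance differences between groups.

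**The concern.** Randomisation protects a comparison of patients allocated over the same period. Here the early pseudoephedrine arm is removed and its randomised counterpart kept. Anything that differed between patients before and after #43 (case mix, staff, pain reporting, otoscopy grading) therefore falls on the placebo side only. That is a systematic difference, not a chance one. The capsule's timing and the allocation ratio also changed at that same point. The manuscript dates the study May 2021 to July 2023, so there was time for drift. A period effect would bias the primary risk difference and its test, and the seven covariates would remove it only so far as they happened to explain it.

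The second, lesser matter is the adjusted model. Eight slopes on few events, reduced by a rule that looks at the treatment estimate, is unlikely to deliver the precise and unbiased estimate that the section aims for. The pre-treatment pain and Teed scores, which were collected and are the natural covariates for those outcomes, are not on the list.

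**Working it through.** **1. The plan's sample size.** Inputs from both Statistical analysis sections: 32% v 8%, alpha 0.05, power 0.80 (two-sided assumed; sidedness is not stated).

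n = [1.960 x sqrt(2 x 0.20 x 0.80) + 0.842 x sqrt(0.32 x 0.68 + 0.08 x 0.92)]^2 / 0.24^2 = 42.4

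That is 43 per group against the stated 42, so the figure reproduces closely.

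**2. Who is concurrent with whom (planned numbers, Protocol section).**

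| Enrolment | Placebo | Pseudoephedrine |
|---|---|---|
| #1-42 | 21, analysed | 21, excluded |
| #43-105 | 21, analysed | 42, analysed |

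So 21/42 = 50% of analysed placebo patients, and none of the analysed pseudoephedrine patients, come from the first period.

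**3. Effect of a period difference when the drug does nothing.** Assumptions: late event rate 20% in both arms (the midpoint of 32% and 8%), with early placebo patients shifted on the logit scale. The pooled placebo rate is (early + late)/2, so the risk difference (pseudoephedrine minus placebo) is biased by half the period difference, with the sign reversed. Rejection rates are exact binomial sums for chi-square, or Fisher where an expected count is below 5.

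| Log-odds shift | Early rate | Bias in risk difference | Rejection, 42 v 42 | Rejection, #43 onward |
|---|---|---|---|---|
| 0 | 20.0% | 0 | 5.2% | 3.9% |
| +0.4 | 27.2% | -3.6 points | 7.0% | 3.9% |
| +0.7 | 33.5% | -6.7 points | 11.4% | 3.9% |
| -0.7 | 11.0% | +4.5 points | 8.3% | 3.9% |

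In simulation with assumed covariates, the backward-selected logistic model rejects in 8%, 13% and 10-11% of null trials under the three shifts, so adjustment for the listed variables does not help.

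**4. Price of restricting to #43 onward, at 32% v 8%.**

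- Risk-difference half-width, 42 v 42: 1.96 x sqrt(0.32 x 0.68/42 + 0.08 x 0.92/42) = 16.3 points. With 21 placebo patients: 21.6 points.
- Exact power: 82.2% against 63.0%.

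**5. Size of the logistic model.** Expected events: 42 x 0.32 + 42 x 0.08 = 16.8 (95% range 10 to 24). Treatment plus seven covariates is at least eight slopes: 16.8/8 = 2.1 events per slope. The modelled outcome is not identified, so the count could differ: 42 x (0.10 + 0.025) = 5.25 events at an assumed 10% v 2.5%, or 42 x (0.50 + 0.25) = 31.5 at 50% v 25%.

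**6. Behaviour of that model (simulation).** Assumed: one continuous and six binary covariates, with several effect sizes and readings of the removal rule. At the planning rates:

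- The starting model cannot be estimated in roughly 4-11% of trials.
- With no covariate effects, the true log odds ratio is ln[(0.08/0.92)/(0.32/0.68)] = -1.69. The mean estimate is about -1.94 to -1.99 from the full model and -1.85 to -1.91 after selection.
- Null rejection is about 5-8% after selection, against 4.5-5.9% for the full model.

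At about 5 events, 64-73% of starting models cannot be estimated. At about 32 events, fewer than 0.5% fail, and the selected estimate averages -1.30 to -1.34 against -1.21.

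A Firth model with all seven covariates plus a baseline score and no selection averages -1.69 with no covariate effects. It averages -1.81 against -1.81 with moderate effects and -2.00 against -1.98 with strong ones. It rejects in 4.0-5.2% of null trials and has 76-82% power.

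**The case against.** **On period.** The documents report no shift between periods. The manuscript gives a constant compression rate, standardised patient education, and the same physician grading each patient before and after treatment. Reuse of the early placebo patients was set out in a dated revision. A reader might infer that the primary result is biased. The documents do not support that: the shifts above are assumptions, and with no shift the pooled test is sound at 5.2%. What stands is that nothing in the plan would reveal a shift if there were one, although a check is available from data in hand.

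**On the model.** It is secondary, its candidate list is named, treatment is always retained, and removal is not by p-value. A reader might infer that selection badly inflates false positives or causes the exaggeration. Neither follows. Inflation is modest, and selection moves the estimate back towards the truth; the excess is already present in the unselected maximum-likelihood fit.

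**On the outcome and the two routes.** It would be too strong to say that the documents name no outcomes: both Statistical analysis sections list them. The gap is which of them is modelled, and how Teed score, for which no cut-point is given, becomes binary. The two model-building routes read as an earlier plan and a later report. That is a detail to explain and does not by itself show a wrong analysis.

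**On the baseline scores.** Limitations relies on the pre-treatment examination and pain score to deal with pain-scale bias, but does not promise to adjust for them. Nor would a model with only treatment and the matching score be better. Oxymetazoline rescue has no such score. In simulation, with one prognostic covariate 30 or 50 points commoner in early placebo patients, the one-score Firth model has null mean log odds ratios of -0.12 and -0.23. The seven-covariate Firth model gives +0.03 and 0.00.

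**Conclusion.** The concern holds, mainly as a point about the primary comparison. By the plan's own counts, half the placebo group is non-concurrent with all analysed pseudoephedrine patients, and no analysis addresses it. Whether this matters in the data is unknown. A moderate assumed shift raises the false-positive rate from 5.2% to between 7.0% and 11.4%, with a bias of about 4 to 7 points either way; the comparison from #43 onward stays at 3.9%.

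The sparse, selected logistic model is a lesser defect: a somewhat exaggerated odds ratio and occasional failure to fit, with modest effect on error rates and none on the primary test. The model figures depend on assumed covariate effects and on the planning event rates, since no observed counts are given. Confidence is medium. The changes are cheap and should be made.

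**What to change.** 1. Report the primary comparison, and the adjusted model, also for enrolment #43 onward (42 v 21). State whether the conclusion depends on the early placebo patients. The patients can be identified because each was "assigned a consecutive study number starting with the number one". The pooled 42 v 42 result can remain the main one. A period term added to the pooled model would draw the treatment contrast from essentially the same concurrent patients and use another parameter.

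2. Replace backward selection with one Firth penalised logistic model containing treatment, the seven listed covariates and, for pain and Teed outcomes only, the matching pre-treatment score. Use penalised-likelihood tests and intervals, because the Wald standard error is 5-11% too small at the design effect. State which binary outcome or outcomes are modelled and the Teed cut-point if Teed is one. Explain the change from the protocol's stepwise route. The backward-selected model may stay as exploratory.

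3. Label all of this post hoc, since the manuscript describes completed work.

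**Cost.** Text edits and a re-analysis of existing data. The restricted comparison is less precise (half-width 21.6 v 16.3 points; power 63% v 82%), so a non-significant result there is weak evidence against the pooled finding; the two estimates should be compared, not only their p-values. The restricted adjusted model would rest on about 21 x 0.32 + 42 x 0.08 = 10.1 events and will be imprecise. The fixed Firth model has slightly lower power (76-82%), and the baseline score adds little if nearly all patients score 0.

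### If the drug works as assumed, the backward covariate rule tends to move the adjusted odds ratio away from the null even without confounding, and no adjusted effect is given as a risk difference

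*Combined protocol and SAP*

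**What the plan says.** The adjusted analysis is described in Materials and Methods, Statistical analysis. It is a logistic regression with seven candidate baseline variables: age, sex, chamber pressure, history of obstruction, sinus disease, smoking and inpatient status. The aim is stated: "We used backward selection, aiming for a precise and unbiased estimate of the pseudoephedrine effect". The retention rule follows: "We removed only variables whose removal would not change this estimate by >10% or increase the standard error by >20" per cent. The text does not say whether the two thresholds apply to the odds ratio or to the log odds ratio.

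The unadjusted effect is on another scale. The protocol's Statistical analysis section says: "We will calculate 95% confidence intervals for the difference in frequencies between groups using normal binomial approximation". Materials and Methods repeats this, and the trial was sized on that contrast: "Our sample size, based on power 0.8, significance 0.05, and effect size 8% versus 32%, was 42 patients in each group". No adjusted risk difference is described. The protocol's own section plans stepwise model building and gives no threshold, so the rule appears only in the manuscript methods.

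**The concern.** A change-in-estimate rule treats any shift above 10% on removing a covariate as a sign of confounding. In logistic regression that inference is unsafe. The odds ratio is non-collapsible, so dropping a prognostic covariate that is perfectly balanced between arms still changes it. With few events, the fitted odds ratio also moves away from the null as terms are added, even when those terms are noise. The standard-error clause is meant to protect precision, but removing a covariate from a logistic model normally lowers the standard error of the treatment coefficient, so the clause has almost nothing to act on.

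At stake is how the supporting analysis is read. An adjusted odds ratio stronger than the crude one invites the conclusion that the crude comparison was biased against the drug. There is no adjusted figure on the scale of 8% versus 32% against which to check that.

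**Working it through.** **Inputs from the documents.** Risks of 32% (placebo) and 8% (pseudoephedrine), alpha 0.05 (two-sided assumed), power 0.80, 42 per group in the comparison ("Overall, we need 42 with placebo and 42 with well-timed Sudafed based on our power calculation"), seven candidate covariates. **Assumed, because the documents give none:** covariate prevalences and covariate–outcome odds ratios.

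**1. The plan's own figure.** Two proportions, pooled variance under the null, no continuity correction:
n = [1.960·√(2·0.20·0.80) + 0.8416·√(0.32·0.68 + 0.08·0.92)]² / 0.24² = (1.1087 + 0.4542)² / 0.0576 = 42.4, that is 43 per group. Power at 42 is 0.796. The stated 42 is reproduced to within rounding.

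**2. Scale and information.** Marginal odds ratio = (0.08/0.92)/(0.32/0.68) = 0.185; log = −1.689; risk difference = −0.24. Expected events = 42·0.32 + 42·0.08 = 16.8. Treatment plus seven single-term covariates is 8 parameters, so 16.8/8 = 2.1 events per parameter.

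**3. Standard-error clause.** The crude standard error of the log odds ratio is √[1/(42·0.32·0.68) + 1/(42·0.08·0.92)] = 0.658. With one balanced covariate of prevalence 30%, the ratio of reduced-model to full-model standard error is 0.991, 0.975, 0.944 and 0.905 for covariate odds ratios 2, 3, 5 and 8. Removal lowers it each time.
- In simulation on the log scale, the clause fired in 0 of about 116,000 removal checks. A separate run with covariates of odds ratio 5 gave 6 of 76,361.
- On the odds-ratio scale, the standard error is the odds ratio times the log-scale standard error. If the log-scale value does not rise, a 20% rise needs the odds ratio itself to rise by more than 20%, so the 10% clause has already acted. In simulation such rises occurred in 0.7% to 17% of first-step removals, and never without a 10% trip.

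**4. The 10% clause under exact balance.** For covariate odds ratio R and prevalence 0.3, solve 0.7·expit(a) + 0.3·expit(a + ln R) = risk in each arm. The conditional log odds ratio is the difference between the two values of a. Example, R = 4: a = −1.230 (placebo) and −3.042 (drug). The conditional log odds ratio is −1.812, odds ratio 0.163. Removing the covariate changes the odds ratio by 0.1848/0.1634 − 1 = 13.1% and the log odds ratio by 1 − 1.689/1.812 = 6.8%.

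| Covariate odds ratio | Conditional odds ratio | Change in odds ratio | Change in log odds ratio |
|---|---|---|---|
| 2 | 0.180 | 2.8% | 1.6% |
| 3 | 0.171 | 7.8% | 4.2% |
| 4 | 0.163 | 13.1% | 6.8% |
| 5 | 0.156 | 18.5% | 9.2% |
| 6 | 0.149 | 23.9% | 11.3% |

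Non-collapsibility alone therefore trips the clause from about odds ratio 4 on the odds-ratio scale and about 6 on the log scale. The risk difference stays at −0.24 throughout.

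**5. The same at 42 per arm.** With one covariate of prevalence 50% exactly balanced in the sample, removing it trips the odds-ratio version in 36% of data sets at covariate odds ratio 3 and 66% at 5. The log version trips in 12% and 33%.

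**6. The full rule, 42 v 42, true risks 32% and 8%, no confounding.**

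| Covariates (assumed) | Crude median | Log rule | Odds-ratio rule | True conditional |
|---|---|---|---|---|
| Two with odds ratio 3 | 0.172 | 0.138 | 0.122 | 0.160 |
| All noise | 0.172 | 0.164 | 0.154 | 0.185 |

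In the first row, removing both prognostic covariates moves the true log odds ratio from −1.835 to −1.689, only 8.0%. The movement under the log rule therefore also needs chance imbalance and sparse data. The second row has no non-collapsibility, yet it drifts.

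**7. Where the drift stops.** With risks of 32% in both arms, the median selected odds ratio was 0.99 to 1.07. With 5,000 per arm, moderate covariates and the log rule, nothing was retained and there was no drift.

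**8. The alternative.** The standardised risk difference averaged −0.241 against −0.242 crude. Its SD was 0.082 to 0.087 against 0.081 to 0.083. Moving the 10% rule onto this quantity still retained a covariate in about 28% to 45% of unconfounded trials.

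**The case against.** Several points on the other side stand.

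- **Non-collapsibility is not the whole cause.** A reader might infer that it explains the drift. On the log scale it needs a strong covariate, and part of the drift is small-sample bias. Adjusting for chance imbalance in a prognostic covariate is legitimate.
- **Confounding is possible here.** A reader might infer that every 10% shift is spurious. The documents do not support that: 21 of the 42 placebo patients were enrolled before the timing and allocation change, while all analysed pseudoephedrine patients came after it. Some adjustment is reasonable.
- **The scales are not wholly incomparable.** A crude odds ratio can be computed from the reported frequencies, and a conditional odds ratio is a valid estimand. What fails is the claim that the selected odds ratio is a precise and unbiased version of the effect.
- **An inert clause does no harm in itself.** True, but it does not provide the precision that the text claims.
- **Primary inference is unadjusted.** The chi-square or Fisher test and the risk-difference interval do not depend on this rule. This limits the importance of the point but does not remove it.

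**Conclusion.** The point holds in a limited form. If the drug works as assumed, the rule tends to give an adjusted odds ratio further from the null than the crude one, and it can overshoot the true conditional value: 0.172 to 0.138 or 0.122 against 0.160 with two covariates of odds ratio 3. The size depends on assumed covariate strengths and on which scale the 10% refers to. It is a tendency across trials, and chance imbalance can move a single trial either way.

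A reader might infer that the rule manufactures an apparent benefit or undermines the trial's main result. The documents and the check do not support that. There is no systematic drift under no effect, and the primary comparison stands apart from the adjusted model. This is a worthwhile, inexpensive correction to a supporting analysis.

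**What to change.** In Materials and Methods, Statistical analysis:

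- Replace the backward change-in-estimate rule, including its standard-error clause, with a fixed covariate list. Take it from the seven named variables, choose it without looking at the treatment estimate, and keep it short given about 17 expected events.
- Report the adjusted effect as a standardised risk difference. Fit the logistic model, predict each analysed patient's risk on pseudoephedrine and on placebo, average the difference, and give a bootstrap or delta-method 95% CI. Place it beside the unadjusted risk difference.
- Keep the odds ratio as a supporting figure only.
- Do not move the 10% rule onto the risk difference, since it still trips often without confounding.

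**Cost.** A small reanalysis with no new data. The adjusted effect will look less strong than the odds ratio suggests. Precision falls slightly if the covariates are not prognostic (SD 0.087 against 0.083 with all seven included).
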